6.2.2 Secondary outcome

Frequencies of individual AE.

7.0 Measures taken to minimize bias:

7.1. Randomization sequence generation:

The randomization sequence will be generated at the Clinical Data Management Centre (CDMC) at Vellore, India using SAS software. The randomization sequence will use 25% of blocks of 4 subjects, 25% of blocks of 6 subjects and 50% blocks of 8 subjects. (Refer SOP Randomization, No: 05 / 02).

In addition, subsets of study participants for additional immunological assessment from the Vadu site will be selected consecutively after the above allocation. Two randomization lists of size 552 with blocks of size 2 and two outcomes (blood draw, no blood draw) have been generated to cover each assessment (day 28 or 364). The same list is used for both study arms. The block randomization will ensure that very close to half are selected for the extra blood draws. There may be some small imbalances between the numbers from each arm selected for the extra examination. (Refer SOP Randomization, No: 05 / 02).

7.2 Allocation concealment:

Treatment allocation will not be able to be determined until the moment of assignment. A website will be created, which can be accessed only by the Randomization Manager at KEM Hospital using a username and password. The website provides access to an application that assigns the treatment allocation. The Medical Officers at the study sites will call the KEM hospital to get the allocation as and when the subject gets recruited into the study. Upon receiving the call the KEM hospital, the Medical Officer at the study site needs to provide the site from which he is calling. Upon receiving the site name, the Operator at the KEM hospital chooses the site on the web page. Then, on the next screen of the web page he/she needs to provide the initials of the child (first name, middle name and the last name), child's date of birth, subject identification number (ID). These are input variables, which will be stored in the database at Vellore. In order to avoid transcribing errors in the entry, the operator needs to retype the subject ID again.

When a unique study ID has been confirmed the person clicks the 'Randomization' button. The next screen gives the allocation as either, 'AEROSOL' or 'SUBCUTANEOUS'. The system records, in a separate database, the details of study site, child's names, Subject ID number, allocation, date and time of randomization. The randomization database will be maintained in Access as backend. This database will be maintained at the CDMC and the backup will be maintained at the backup server which is kept at the Pharmacology Department Museum (old name: Booshnam Moses Computing Center) (Refer SOP Randomization, No: 05 / 02).

SOP VEL 1/1:	Statistical Analysis Plan	Page 5 of 61	
September 11, 2012			

7.3 Blinding of Laboratory Staff:

Staff at the study sites and participants' parents will know which treatment has been given. To minimize bias in the assessment of immunogenicity outcomes, laboratory staff will not know the treatment allocation or the order of specimens that they will analyze.

In order to blind laboratory staff to the specimen collection time (day 0, day 28 day 91 or day 364) for the subjects, a single digit random number will be generated and concatenated with the subject ID. This is called the Lab Code. Thus a subject will have a unique Lab Code of 5 digits.

The laboratory will be provided with lists of 22 pairs (day 0 and day 91) of specimen Lab Codes, which will be randomly ordered. Similarly, for the specimens of children who will be followed up at day 28 and day 364, the laboratory will be provided with lists of randomly ordered Lab Codes.

8.0 Sample size:

8.1 Immunogenicity:

The sample size for the primary outcome is determined using the confidence interval (CI) approach, considering where the CI for the treatment effect lies with respect to a pre-specified margin of non-inferiority and the null effect (1).

Total to be enrolled, 2000. This number was based on the following assumptions:

- Significance 2.5%, one sided for non-inferiority, 5% for two sided superiority;
- Non-inferiority margin 5%;
- Power for non-inferiority 90% if true seropositivity is 90% in both arms;
- 20% loss to follow up by day 91, leaving 1600 available for primary analysis.

Sample size for immunogenicity subset:

Those selected for additional testing at day 28 or at day 364 will have ELISA and PRNT test results at these time points as well as at day 0 and 91.

The sample size will be 100 in each arm at each of day 28 and day 364. Based on the estimated variability (Standard deviation) of post subcutaneous vaccination PRNT results of 0.43 on a \log_{10} scale ([name], Health Protection Agency London, personal communication) differences of <1.5 fold in geometric mean titres between aerosol and subcutaneous groups at each time point and between each time point would be able to be detected at a 5% significance level with 80% power.

8.2 Safety:

To estimate proportions with AE in Aerosol and Subcutaneous groups, the sample sizes above give acceptable precision.

SOP VEL 1/1:	Statistical Analysis Plan	Page 6 of 61
September 11, 2012		

Phase II/III	WHO Measles Aerosol Vaccine	Protocol
Clinical Trial	Project	WHO/MAP/IN/002

Table 8.2.1: Range of Precision with	Different Leve	els of Proportions	Experiencing
Event and Numbers of Participants.			

Observed	95% confidence intervals	
proportions	N=800	N=1000
0%	0.00 - 0.46%	0.00-0.37%
1%	0.43-1.96%	0.48-1.83%
2%	1.15-3.23%	1.26-3.07%
5%	3.60-6.75%	3.73-6.54%

The table shows that, if no reactions are observed, the upper 95% confidence interval with a sample size of 1000 is 0.37%, or 1 in 270.

9.0 Data Management and Pre-analysis Statistical Review:

9.1 Data Management:

The data management plan has been developed by the CDMC, Dept., of Biostatistics, Christian Medical College, Vellore. For more details refer to SOP 04/02 Clinical Data Management.

9.1.1 Data Quality Control, Query management and Quality Assurance:

Please refer SOPs Query Generation and Resolution (15/02) and Quality control and Quality assurance (16/02) for details.

9.2 Pre-analysis Statistical Review

This pre-analysis review will be used to make decisions about issues including the exclusion of subjects or data from analysis sets, possible data transformations, and identification of outliers. Important covariates identified in recent research studies might be specified at this stage. The final format of tables will be decided after this review. Decisions taken during the pre-analysis review will be documented.

The steps to be taken in the pre-analysis review are as follows:

1. Each database (e.g. laboratory data, AE data, etc.) will be imported to SAS software format.

SOP VEL 1/1:	Statistical Analysis Plan	Page 7 of 61
September 11, 2012		

Phase II/III	WHO Measles Aerosol Vaccine	Protocol
Clinical Trial	Project	WHO/MAP/IN/002

2. Basic frequencies and distribution tables and/or plots will be performed for each variable. For example, histograms will be made for continuous variables, such as age, height and weight, etc.

10.0 Description of Patient Flow and Analysis Datasets:

The flow of participants through the trial and follow up will be described in flow charts, as recommended by the CONSORT group (2). The flow diagrams will describe the numbers at each stage and will summarize reasons for exclusion for a 'per-protocol' dataset and an 'intention to treat' dataset (Figures 11.12.7.1 to 11.12.7.3). Tables describing the numbers excluded at each stage will also be produced (Tables 11.12.5.1 to 11.12.5.5B).

11.0 Statistical Methods:

In this section we first describe the method to be used for the analysis of the primary outcome. We then describe the principles and methods to be used for descriptive and comparative statistical analyses and tables that will be used to report these.

11.1 Analysis of the primary outcome:

The figure shows how the differences in the proportions with the primary outcome and the two sided 95% CI will be interpreted.

Figure 11.1.1:

95% CI for differences in proportions seropositive (Aerosol - Subcutaneous)

SOP VEL 1/1:	Statistical Analysis Plan	Page 8 of 61
September 11, 2012		

Phase II/III	WHO Measles Aerosol Vaccine	Protocol
Clinical Trial	Project	WHO/MAP/IN/002

In Figure 11.1.1 non inferiority has been demonstrated for scenarios 1), 2) and 3) since the lower limit of the 95% CI is above -5%. In addition for scenario 3) superiority has been shown because the lower limit does not include 0%. For scenarios 4) and 5) non-inferiority has not been demonstrated and for scenario 5) aerosol is inferior as the upper limit does not include 0%.

Note: Using the Wilson score method, 95% CI will be calculated using SAS software. (Newcombe 1998, Agresti et al 1998)

11.2 Per-Protocol (PP) Analysis Set:

This is the analysis set that will be used for the primary analysis of efficacy. The PP analysis set includes all children with an interpretable result from the blood sample scheduled for 91 days (-7 to +28 days), and without major protocol deviations. Study participants remain in the study up to until the point at which they drop-out or deviate from the protocol (Protocol section 12.0).

Protocol deviations include:

- Study participant incorrectly entered the study, e.g. did not meet age criteria;
- Study participant should have been withdrawn during study but was not;
- Study participant did not receive the vaccine according to the arm to which he / she was randomized;
- Study participant received the wrong dose of vaccine;
- Study participant received a dose beyond the recommended multi-dose vial policy
- Wrong subject ID randomized
- Wrong Subject ID
- Home Visit and Clinic visit on same date
- Visits outside the window period
- Wrong labelling of the CRF
- Wrong labelling of vials
- Informed consent issue

The assessment of long-term immunogenicity in the subset of participants from Vadu, includes children with an, interpretable result from blood sample scheduled for 364 days (-7 to +28 days), and without major protocol deviations.

11.3 Modified Intention to Treat (ITT) Analysis Set:

The 'intention to treat' analysis will be conducted as a secondary analysis. In a noninferiority trial such as this, the intention to treat analysis is more likely than the perprotocol analysis to give a type I error (falsely claiming non-inferiority) because this kind of analysis tends to minimize differences between the two treatments (1).

The ITT analysis set includes assessments up to 91 days (-7 to +28 days) post-vaccination. All study participants will be included in the group to which they were randomized.

SOP VEL 1/1:	Statistical Analysis Plan	Page 9 of 61
September 11, 2012		

11.4 As Treated Cohort Analysis set:

The primary efficacy analysis for safety includes all children vaccinated, according to the route of vaccination that they received and with at least one safety assessment.

In addition, we will summarize explicitly any severe reactions or serious adverse events (SAE) in children vaccinated by the wrong route.

11.5 Timing of Analyses:

The primary efficacy analysis will be conducted after the last enrolled participant completes the day 91 follow up visit.

Every 3 months the data will be analyzed and a report will be made available for the DSMB. This report will focus on safety.

11.6 Method for Handling Missing Data:

For the primary efficacy analysis there is no plan to impute data values for participants who do not complete follow up visits.

For the PP dataset, missing values will be treated as missing at random. However, preliminary analyses such as age, sex, baseline immunogenicity distribution will be studied between the two groups to examine the validity of this assumption.

For the assessment of immunogenicity, missing values (e.g. no blood taken) are treated as if they are missing at random. The OD values for blood samples taken outside the specified time limits will be treated as missing values.

Note that missing values at 91 days post-vaccination and at other time points will be considered for further analyses. The missing information will be handled by best and worst case scenario methods. Where blood specimens are taken outside the recommended time interval, these results will still be used.

11.7 Significance Level:

This is a non-inferiority trial and the confidence interval approach will be used to determine the trial outcome. For additional analyses, such as those adjusting for covariates, we will not use a fixed 'statistical significance' level for reasons described by Sterne and Davey Smith (3). For analyses that require the calculation of p values, we will base our interpretation on examination of the effect size, confidence interval and p value.

11.8 Safety:

We will estimate the proportions (with 95% CI) of AE in each arm according to the definitions of the primary and secondary safety outcomes (Refer section 8.7 in the protocol).

SOP VEL 1/1:	Statistical Analysis Plan	Page 10 of 61
September 11, 2012		

11.9 Covariates to be examined:

Covariates of interest are as follows:

Baseline: Age in months, sex, usual health care provider, heart rate, respiratory rate, temperature, height for age, weight for age, any abnormality discovered on systemic examination, pre existing medical conditions (Table 11.12.6.1B)

Others: Observations during vaccination (Table 11.12.6.1D)

The distribution of the baseline covariates by study arm will be described, but not formally tested as randomization will have ensured that any differences are chance differences. For the main comparison of the study arms adjustment for these covariates is not necessary. To investigate the effect of these covariates on study end-points multivariable logistic regression (for binary end points) or normal errors regression (on logged antibody levels) will be performed. Study arm will be included in these analyses and interactions examined as given in section 11.11.

11.10 Sub-group analyses:

No sub group analyses have been planned.

11.11 Interactions with study arm:

Potential interactions will be examined for the following co-variates: sex, age, crying during measles vaccination, and acute respiratory infection.

11.12 Descriptive Analyses:

11.12.1 Distributions of continuous variables and any agreed transformations:

Mean, standard deviation, median, and interquartile range will be generated for continuous variables. The PRNT values will be doubled if the value is >20,000. The PRNT values will be \log_{10} transformed for further analyses such as GMT and 95% CI. Results at the lower limit of the assay will be assigned a value of 10. OD values will also be \log_{10} transformed to calculate geometric means and perform regression. Any OD results of <0.01 will be assigned a value of 0.005 prior to \log_{10} transformation.

11.12.2 Distributions of binary and categorical variables:

Frequency distributions will be shown for binary and categorical variables. The categories will be checked against the Annotated CRF.

11.12.3 Outliers:

For \log_{10} PRNT values, checks for outliers will be performed prior to the statistical analysis as part of the data checking. The outliers will also be examined using standardized residuals >3 when looking at \log_{10} PRNT values.

SOP VEL 1/1:
September 11, 2012

Phase II/III	WHO Measles Aerosol Vaccine	Protocol
Clinical Trial	Project	WHO/MAP/IN/002

11.12.4 Flow of Numbers:

The flow of participants through the trial and follow up will be described in flow chart, as recommended by the CONSORT 2010 guidelines and guidance, Reference (3).

SOP VEL 1/1:	Statistical Analysis Plan	Page 12 of 61
September 11, 2012		
Phase II/III	WHO Measles Aerosol Vaccine	Protocol
----------------	-----------------------------	----------------
Clinical Trial	Project	WHO/MAP/IN/002

Table 11.12.1: Number of children enrolled and allocated to vaccination by study area, stu	dy
arm, sex	

Study area	Assess for aligibility given for	ParentAcceptwillingenrolment	Allocated to	Aerosol Arm			Subcutaneous Arm				
	engionity	Vaccinating	0		inter vention	Boys	Girls	Total	Boys	Girls	Total
Alandi											
Chakan											
Nhavara											
Pabal											
Shel Pimpalgaon											
Talegaon Dhamdhere											
Vadu											
Wagholi											
TOTAL											

SOP VEL 1/1:	Statistical Analysis Plan	Page 13 of 61
September 11, 2012		

Phase II/III	WHO Measles Aerosol Vaccine	Protocol
Clinical Trial	Project	WHO/MAP/IN/002

11.12.5 Patient Data Listings:

The data listings of discontinued subjects and the details of completion of enrolled subjects at various time points, the reasons for drop out and the distribution of excluded subjects for efficacy analyses are presented from table 11.12.5.1 to 11.12.5.5B.

 Table 11.12.5.1: List of all patients discontinued from the study after enrolment

Subject ID	Study arm (AER, SC)	Days in trial post- vaccinatior	Age	Gender	Adverse events	Major reason discontinued	Visit	AE / Severity	Last visit before discontinuation

Legend:

AER - aerosol vaccination; SC - subcutaneous vaccination

SOP VEL 1/1:	Statistical Analysis Plan	Page 14 of 61
September 11, 2012		

Table 11.12.5.2: Number of subjects enrolled and followed up at major time points by study area

	Study arm to which participants were randomly allocated					
Primary Health Centre and Time point	Aerosol, n =	Subcutaneous, n =				
	(% allocated to	(% allocated to				
	intervention)	intervention)				
Alandi						
Day 0 - Allocated to intervention						
Day 0 - Received allocated intervention						
Day 28						
Day 91						
Chakan						
Day 0 - Allocated to intervention						
Day 0 - Received allocated intervention						
Dav 28						
Day 91						
Nhavare						
Day 0 - Allocated to intervention						
Day 0 - Received allocated intervention						
Day 28						
Day 91						
Pabel						
Day 0 - Allocated to intervention						
Day 0 - Received allocated intervention						
Dav 28						
Day 91						
Shel Pimpalgaon						
Day 0 - Allocated to intervention						
Day 0 - Received allocated intervention						
Day 28						
Dav 91						
Talegaon Dhamdhere						
Day 0 - Allocated to intervention						
Dav 0 - Received allocated intervention						
Day 28						
Dav 91						
Vadu						
Dav0 - Allocated to Intervention						
Dav0 - Received allocated Intervention						
Day 28 - clinical assessment						
Day 28 - blood specimen*						
Dav 91						
Dav 364 - clinical assessment*						
Dav 364 - blood specimen*						
Wagholi						
Day 0 - Allocated to Intervention						
Day 0 - Received allocated Intervention						
Day 28						
Day 91	1					

Legend: *Applies to Vadu subset only

Phase II/III	WHO Measles Aerosol Vaccine	Protocol
Clinical Trial	Project	WHO/MAP/IN/002

Decesso	Study arm to which the participants were randomly allocated						
Reasons	Ae	rosol	Subcutaneous				
	n	(%)	n	(%)			
Screening failure							
Withdrawal of consent							
Refusal							
Loss to follow up							
SAE other than death							
Death							
Others							

 Table 11.12.5.3: Summary of reasons for discontinuation in the clinical trial

Phase II/III	WHO Measles Aerosol Vaccine	Protocol
Clinical Trial	Project	WHO/MAP/IN/002

Table 11.12.5.4: Summary of protocol deviations that occurred during the clinical trial

Reasons		Study arm to which participants were randomly allocated					
Ktasons	Ae	rosol	Subcu	Subcutaneous			
	n	(%)	n	(%)			
Incorrectly provided vaccination							
Aerosol							
Subcutaneous							
Incorrectly entered the study, e.g. inappropriate age							
Should have been withdrawn but was not							
Received the wrong dose of vaccine (e.g. too little or too much)							
Received a dose beyond the recommended multi- dose vial policy							
Other violation of study protocol							
Wrong subject ID randomized							
Subject ID interchange							
Home visit and clinic visit on same date							
Visit outside the window period							
Wrong labelling of the CRF							
Wrong labelling of vials							
Informed consent issue							
Total number of Protocol Deviations							
Number of subjects having protocol deviations							

Phase II/III	WHO Measles Aerosol Vaccine	Protocol
Clinical Trial	Project	WHO/MAP/IN/002

Table 11.12.5.5: Study participants excluded from the per protocol analysis of Immunogenicity

Subject ID	Allocated intervention	Days in trial post- vaccination	Age	Sex	Reason for exclusion

Phase II/III	WHO Measles Aerosol Vaccine	Protocol
Clinical Trial	Project	WHO/MAP/IN/002

11.12.6: Distributions of socio-demographic, baseline health and disease status and anthropometric variables

Table 11.12.6.1A: Baseline demographic characteristics of studyparticipants by allocated intervention

	Allocated intervention				
	Α	erosol	Subcutaneous		
Baseline characteristics	n	(% of number allocated)	n	(% of number allocated)	
Age in months					
9 to 9.99					
10 to 10.99					
11 to 11.99					
Sex					
Male					
Female					
Usual health care provider					
Government					
Private					
Non-governmental organization					
Other					

Table 11.12.6.1B: Baseline health and disease status of study participants

 by allocated intervention

		Allocated Intervention			
	Aerosol		Subcutaneous		
Findings		(% of number allocated)	n	(% of number allocated)	
Pre-existing medical condition					
Significant medical history since birth					
Significant illness in the last three months					
Regular medication for more than one month					
Concomitant medications received during the last four weeks					

SOP VEL 1/1:	Statistical Analysis Plan	Page 19 of 61
September 11, 2012		

Phase II/III	WHO Measles Aerosol Vaccine	Protocol
Clinical Trial	Project	WHO/MAP/IN/002

Table 11.12.6.1C: Baseline anthropometry and vital signs of study participants by allocated intervention

	Allocated intervention				
Findings		Aerosol	Sub	Subcutaneous	
	mean	(SD)	mean	(SD)	
Heart rate					
Respiratory rate					
Temperature					
	n	(% of number allocated)	n	(% of number allocated)	
Any abnormality discovered on systemic examination					
Height for age below normal range					
Weight for age below normal range					

Table 11.12.6.1D: Observations during vaccination study participants by Allocated

 Intervention

	Allocated Intervention			
	Aerosol		Subcutaneous	
Observations	n	(% of number allocated)	n	(% of number allocated)
Child calm during vaccination				
Child struggling during vaccination				
Child breathing shallow during vaccination				
Child crying during vaccination				
Child holding his/her breath during vaccination				
Child coughing during vaccination				
Child exhibited abnormal behaviour during vaccination				

SOP VEL 1/1:	Statistical Analysis Plan	Page 20 of 61
September 11, 2012		

Phase II/III	WHO Measles Aerosol Vaccine	Protocol
Clinical Trial	Project	WHO/MAP/IN/002

Figure 11.12.7.1:

Immunogenicity: Flow Chart for Per-Protocol (PP) Analysis

SOP VEL 1/1:	Statistical Analysis Plan	Page 21 of 61
September 11, 2012		

Phase II/III	WHO Measles Aerosol Vaccine	Protocol
Clinical Trial	Project	WHO/MAP/IN/002

Figure: 11.12.7.2

Immunogenicity: Flow Chart for Intent to Treat (ITT) Analysis

SOP VEL 1/1:	Statistical Analysis Plan	Page 22 of 61
September 11, 2012		

Phase II/III	WHO Measles Aerosol Vaccine	Protocol
Clinical Trial	Project	WHO/MAP/IN/002

Figure: 11.12.7.3

Safety: Flow Chart of "As Treated" Analysis for Safety

SOP VEL 1/1:	Statistical Analysis Plan	Page 23 of 61
September 11, 2012		

12.0 Efficacy Analyses:

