8.5.1.12 Visit 12, AE follow up- clinic visit (day 91 +/- 7 days)

Purpose of visit: Ascertainment of primary trial outcome in all participants.

Procedures:

• As described in visit 6 (above). Structured questionnaire for adverse events, medical examination, including directed neurological examination, recorded in CRF (SOP VAD 5/1). Blood sample from all participants (SOP HPA 1/1)

Figure 3: Study Flowchart for Follow-up Visits 3 to 16: Day 3 to 91

8.5.1.13 Visits 13 and 14, home visits for all children enrolled in Vadu district (day 182 and 252, Figure 4)

Purpose of visit: To collect information about adverse events.

Procedures:

- As described in visit 3 (above).
- Fieldworkers give parents/guardians children appointment for visit 15 at PHC.

8.5.1.14 Visit 15, home visit for subset of children enrolled in Vadu district (pre-Visit 16)

Purpose of visit: To remind parents/guardians of the clinic appointment.

Procedures: Fieldworkers will ensure that parents/guardians have arranged transport to the PHC, and tell them that the costs of travel and time spent on the visit will be reimbursed.

8.5.1.15 Visit 16, clinic visit for all children enrolled in Vadu district (day 364 +/-7 days)

Purpose of visit: Ascertainment of adverse events in all enrolled children in Vadu district and, for selected subset, to draw blood for antibody levels one year after vaccination.

Procedures:

• Clinic visit: As described in visit 6 (above). Structured questionnaire for adverse events, medical examination, including directed neurological examination, venepuncture, recorded in CRF (SOP HPA 1/1).

Figure 4: Study Flowchart for Follow-up Visits 13 to 16: Day 182 to 364.

Ínfants from Vadu only.

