12.1.2 Immunogenicity

Primary analysis is to calculate the 2-sided 95%CI for the difference in proportion seropositive at day 91. If lower limit of difference greater than -5% then conclude non-inferiority. If lower limit of difference greater than 0% then conclude superiority.

Secondary analyses will include calculation of 95% confidence intervals for seropositivity, seroconversion and geometric means as well as multivariable logistic and normal errors regression adjusting for covariates.

Secondary analysis of factors associated with seroconversion/response, including:

- pre-vaccination titre
- Age (9m,10m,11m) (also look at interaction with intervention)
- Sex (also look at interaction with intervention)
- PHC
- Crying when vaccine given? (also look at interaction with intervention).
- (Another factor we considered before was acute respiratory infection)
- Explanatory variables for stratification of safety profile

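### The primary per-protocol set is not unambiguously defined (late samples, ungraded deviations), and superiority would be concluded from that same set

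*Supplement*

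**What the plan says.** **Sample window.** The protocol schedules the day 91 visit in section 8.5.1.12: "Visit 12, AE follow up- clinic visit (day 91 +/- 7 days". That is days 84 to 98. SAP 11.2 admits to the PP set children with an "interpretable result from the blood sample scheduled for 91 days (-7 to +28 days), and without major protocol deviations", so samples from day 84 to day 119 qualify. SAP 11.3 puts the same -7 to +28 bounds on the ITT set. Among the deviations listed in SAP 11.2 is "Visits outside the window period", with no window named.

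**Out-of-window results.** SAP 11.6 states: "The OD values for blood samples taken outside the specified time limits will be treated as missing values". The paragraph after it ends: "Where blood specimens are taken outside the recommended time interval, these results will still be used".

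**Deviations.** Only major deviations remove a child from PP. The list in SAP 11.2 is introduced simply as protocol deviations. It runs wrong arm and wrong dose together with home and clinic visits on one date and CRF labelling errors. SAP 9.2 leaves exclusions to a documented pre-analysis review and does not mention masking.

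**Superiority.** PP is the primary set (protocol 12.1.1, SAP 11.2). From the primary interval, protocol 12.1.2 says: "If lower limit of difference greater than 0% then conclude superiority". SAP Figure 11.1.1, scenario 3, repeats this. SAP 11.3 argues that ITT tends to shrink differences between arms.

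**The concern.** Two analysts could follow this SAP in good faith and arrive at different primary sets. A child bled on days 99 to 119 meets the sample criterion of SAP 11.2, yet may also have a listed deviation if the unnamed window is the protocol's ±7 days. Whether that deviation is major, and whether a labelling error is, has been left to a later judgement. In an open-label trial such judgements should be made without knowledge of arm or serology, and the SAP does not say that they will be.

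The choice of set for superiority is a separate matter. PP is made primary because it is the cautious set for non-inferiority. The same argument points the other way for superiority, but the rule was not adapted.

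At stake are some power and the credibility of the set on which a licensing conclusion rests.

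**Working it through.** **1. Windows side by side.** Protocol visit: 91 ± 7 = days 84–98, 15 days. SAP analysis window: 91 - 7 to 91 + 28 = days 84–119, 36 days. The band in question is days 99–119, 21 days.

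**2. The plan's own sample size.** Inputs from SAP 8.1: "Significance 2.5%, one sided for non-inferiority, 5% for two sided superiority"; margin 5 points; 90% seropositive in both arms; 90% power; 20% loss; 1600 evaluable of 2000 enrolled.

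- n per arm = (1.96 + 1.2816)² × 2 × 0.9 × 0.1 / 0.05² = 756.5, so 757.
- With a continuity correction, (757/4) × [1 + √(1 + 4/(757 × 0.05))]² gives 797 per arm. That is 1594 evaluable and 1594/0.8 = 1993 enrolled, which matches the stated figures.

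**3. Power if late samples are dropped.** Power = Φ(0.05/√(0.18/n) - 1.96). The drop-out fractions are assumed.

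| Dropped per arm | n per arm | Φ argument | Power |
|---|---|---|---|
| 0% | 800 | 3.333 - 1.96 = 1.373 | 91.5% |
| 5% | 760 | 3.249 - 1.96 = 1.289 | 90.1% |
| 10% | 720 | 3.162 - 1.96 = 1.202 | 88.5% |
| 15% | 680 | 3.073 - 1.96 = 1.113 | 86.7% |

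Exact enumeration with the Newcombe–Wilson interval gives 91.3%, 89.8%, 88.2% and 86.3%.

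**4. When exclusions bias the result.** These are exact calculations with the same interval, starting from 800 per arm.

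- True 90% in both arms, exclusions unrelated to outcome: false aerosol superiority is 2.5%, the nominal rate.
- True 90% in both arms, with 4, 8 or 16 aerosol seronegatives removed and no one else (assumed): 4.9%, 8.9% or 24.4%.
- True 85% v 90%, at the non-inferiority margin, with 6 or 12 aerosol seronegatives removed (assumed): false non-inferiority rises from 2.5% to 5.9% or 12.2%.

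**5. Superiority example.** Lower limit = d - √[(p₁ - l₁)² + (u₂ - p₂)²], where l and u are Wilson limits; the upper limit is analogous.

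- PP 744/800 (93.0%; l₁ 91.02%) v 720/800 (90.0%; u₂ 91.89%): 3.0 - √(1.98² + 1.89²) = 0.26. The interval is +3.0 (0.26 to 5.76), superior.
- Restore 50 per arm at 60% positive on aerosol and 90% on subcutaneous: 774/850 v 765/850 = +1.06 (-1.74 to 3.86), not superior.
- Restore 50 per arm at 90% positive in both: 789/850 v 765/850 = +2.8 (0.15 to 5.5), still superior.

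The reversal therefore depends entirely on the assumed 30-point gap among excluded children.

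**6. SAP 11.6 against 11.3.** The sentence allowing use of out-of-interval specimens sits in a paragraph about further analyses handled by best- and worst-case methods, which protocol 11.5.6 assigns to ITT. But SAP 11.3 bounds ITT at -7 to +28 days as well. Even the favourable reading leaves no defined set in which those results can be used.

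**The case against.** The defence is strong on several points.

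- **Windows.** A visit window narrower than the analysis window is ordinary practice. SAP 11.2 and 11.3 agree on -7 to +28. A reader might infer an outright contradiction, but that requires treating a late visit inside the analysis window as a major deviation, which the SAP does not do.
- **Clerical errors.** A reader might infer that a mislabelled CRF removes a child. The SAP does not say so: only major deviations exclude. The list largely mirrors the reporting table (Table 11.12.5.4), and PP exclusions have their own listing (Table 11.12.5.5). What stands is that nothing is graded. The text is further clouded by the next sentence of SAP 11.2, which refers to children who deviate without the qualifier.
- **Masking.** A reader might infer an unblinded review. SAP 9.2 is silent, and protocol 6.8.1 delays unblinding of day 91 specimens until after database lock. The supportable statement is only that masking is not stated.
- **SAP 11.6.** The two sentences can be read as covering primary and further analyses respectively. That is plausible, but the scope is not written down and SAP 11.3 does not fit it.
- **Superiority.** Protocol 5.1 calls it unrealistic, and intervals for both sets are already planned (Tables 12.1.4A and 12.1.4B). This lowers the weight of the point, but the decision rule remains in the plan and is not tied to ITT.

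**Conclusion.** The point holds as a clarification that should be made; it does not invalidate the primary analysis. The handling of late samples, the meaning of major and the masking of the review are not settled by the text, and superiority is read from the less cautious set on the SAP's own reasoning.

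The cost in power is small: 91.5% falls to 90.1–86.7% if an assumed 5–15% per arm were dropped under the strict reading. The documents give no figure for late samples.

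It would go too far to say that PP is inherently anti-conservative for superiority. Exclusions unrelated to outcome leave the error at 2.5%; inflation needs exclusions linked to both arm and serostatus, and nothing in the documents shows that they will be. If they were, the non-inferiority conclusion would be exposed too, and that matters more here than superiority does.

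**What to change.** 1. In SAP 11.2 and 11.6, state that a day 91 sample within -7 to +28 days is eligible for PP and that a late visit inside that window is not a major deviation. State that samples outside it are excluded from PP and used only in the ITT or sensitivity analysis, and amend SAP 11.3 to match.
2. Mark each listed deviation as major or not. Reserve major for those that can affect serology, eligibility, identity or consent. State in SAP 9.2 that the classification is made masked to arm and serology, before unblinding.
3. Base any superiority statement on the ITT interval. State the non-inferiority conclusion on both PP and ITT.

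The cost is SAP wording only, since both intervals are already tabulated. A superiority claim becomes slightly harder to make.
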